4.7 Comparison: CT-guided Biopsy Pathway

The control arm of the study will consist of CT-guided biopsy, which will be performed by interventional radiologists with expertise in transthoracic needle biopsy and/or fine needle aspiration (as defined by more than 25 procedures performed in the past two years as a department). Procedures will be performed in a dedicated interventional CT scanner with multi-slice capabilities. Patient analgesia with local anesthesia and moderate conscious sedation will be used. Biopsy number, core biopsy vs. fine needle aspiration, use of coaxial needles, and use of rapid on-site cytologic examination will be at the discretion of the proceduralist per local institutional preferences. Procedures will be followed by limited CT scan and/or chest radiograph to exclude pneumothorax if required per local standard of care. The procedure will be deemed non-diagnostic if the proceduralist is unable to reach the nodule or if a complication occurs and therefore no biopsy is obtained.

- 1. Patients not eligible for general deep sedation and general anesthesia and therefore not eligible for bronchoscopy, but potentially eligible for CT-guided biopsy, will be excluded from the study but recorded as such in the CONSORT diagram.**
- 2. Patients randomized who fail to present for their assigned intervention will be considered screen-failure**
- 3. Patients randomized who present for their assigned intervention but do not undergo the procedure for reasons other than for contraindications to the procedure (per institutional policy) will be analyzed as non-diagnostic procedure, and otherwise considered screen-failure. The cause for cancellation will be recorded in the case report form.**

CONFIDENTIAL

See Procedural Flow Chart (Section 14).

4.8 Outcomes

Primary endpoint

The primary endpoint will be diagnostic accuracy, as defined by the rate of technically successful biopsies leading to a definitive diagnosis, comparing the navigation bronchoscopy to the CT-guided biopsy pathway. Definitive diagnoses are pre-defined as any of the following:

- Malignancy on histological samples, **OR**
- Biopsies with abnormal tissue (excluding normal or absence of lung parenchyma) that are followed by a surgical lung biopsy yielding the same histological diagnosis, **OR**
- Specific benign histopathologic finding which accounts for the presence of a lung nodule (specifically including organizing pneumonia, frank purulence, granulomatous inflammation, or other specific benign finding) **AND**
- Absence of malignancy (true negative) over 1 year of longitudinal CT follow-up, defined as:
 - the nodule markedly regresses or resolves on follow-up imaging, **OR**
 - a persistent nodule has not been diagnosed as malignant, **AND**
 - there are no plans for repeat invasive diagnostic procedures through 12 months follow-up.

Biopsies with normal or absence of lung parenchyma, atypia or mild inflammation will be considered non-diagnostic. All diagnoses (from both arms) will be determined by a blinded, independent, expert lung pathologist (i.e. blind to the biopsy technique) and all non-diagnostic biopsy specimens will be reviewed by an independent expert pathologist.

Linear EBUS for lymph node interrogation and staging will be performed in the same procedure after the navigation bronchoscopy for staging purposes as per standard of care.

Secondary endpoints

- Rate of pneumothorax
- Rate of pneumothorax requiring chest tube placement
- Clinically significant bleeding (defined by bleeding requiring intervention)
- Need for hospitalization after procedure
- Duration of the procedure (from bronchoscope in to bronchoscope out for the bronchoscopy arm and from first needle in to last needle out for CT-guided biopsy)
- Procedural factors associated with improved yield (type of biopsy, number of biopsies, use of radial ultrasound, presence of a bronchus sign, biopsy site)
- Need for additional nodule biopsy
- Need for additional procedure for staging

CONFIDENTIAL

- Radiation exposure from fluoroscopy-guided bronchoscopy and CT for CT-guided biopsy
- Need for F-Nav during navigation bronchoscopy
- Adequacy of specimens collected for molecular testing when needed.
- Diagnostic yield, defined as the rate at which histopathology is obtained which explains the presence of a nodule (according to definitions set forth for the primary endpoint) and permits post-biopsy clinical decision-making without need for immediate additional diagnostic procedures.
- Rate at which the biopsy procedure yields a confident clinical diagnosis (including any added yield from endobronchial ultrasound-guided mediastinal and/or hilar lymph node biopsies or microbiologic studies which yield an explanation for a nodule despite non-diagnostic biopsy specimens).

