Primary endpoint	
The primary endpoint will be diagnostic accuracy, as defined by the rate of technically successful biopsies leading to a definitive diagnosis, comparing the bronchoscopy pathway (navigation bronchoscopy) to the CT-guided biopsy pathway. Definitive diagnoses are pre-defined as any of the following:
 
• Malignancy on histology, OR• Biopsies with abnormal tissue (excluding normal or absence of lung parenchyma) that are followed by a surgical lung biopsy yielding the same histological diagnosis, OR• Specific benign histopathologic finding which accounts for the presence of a lung nodule (specifically including organizing pneumonia, frank purulence, granulomatous inflammation, or other specific benign finding) AND• Absence of malignancy (true negative) through 1-year longitudinal CT follow-up, defined as:
◦ The nodule markedly regresses or resolves on follow-up imaging, OR◦ a persistent nodule has not been diagnosed as malignant, AND◦ there are no plans for repeat invasive diagnostic procedures through 12 months follow-up. 
Biopsies with normal or absence of lung parenchyma, atypia and non-specific inflammation will be considered non-diagnostic. All biopsies not diagnostic of malignancy (from both arms) will be centrally reviewed by an independent expert lung pathologist blinded to the biopsy technique, and follow-up diagnosis will be established during routine clinical follow-up after 1 year.

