4.6 Intervention Arm: Bronchoscopy Pathway

The intervention arm will consist of electromagnetic (EMN) navigation bronchoscopy using the Medtronic SuperDimension platform with F-Nav. Patients' available DICOM CT images will be uploaded into the planning software. CTs obtained more than 21 days before the planned procedure, and CT not meeting minimal technical requirements for optimal roadmap planning (adequate CT reconstructions and slice thickness of 1.5mm or less) will be repeated before the procedure. Bronchoscopy will be performed by interventional pulmonologists with expertise in navigation bronchoscopy (as defined by more than 100 procedures performed in the past 2 years, with at least 25 of these performed with F-Nav). Procedures will be performed under general anesthesia with neuromuscular blockade (to facilitate breath holds required for FNAV image acquisition) in a dedicated bronchoscopy suite or operating room. Bronchoscopy will be performed as previously described with confirmation by radial ultrasound.¹⁷ Suggested intraprocedural flow is detailed in the figure in section #14. Radial ultrasound will be used for confirmation only, and not as a navigational tool (i.e. catheters not aligned with the registered target will be considered non-diagnostic). Biopsies will be obtained using a any-gauge needle, with at least 5 passes obtained per nodule. Forceps biopsies, brushings or other biopsy tools will be performed according to the procedure algorithm. Rapid on-site evaluation will be performed to assess for specimen adequacy. All procedures will be followed by fluoroscopy evaluation of the chest to exclude pneumothorax, and, if indicated, ultrasound and/or formal chest radiograph as per standard of care. The procedure will be deemed non-diagnostic if the proceduralist is unable to reach the nodule or if a complication occurs and therefore no biopsy is obtained.

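### The primary endpoint accepts malignancy on histology only, yet both arms may be sampled by methods that yield only cytology, so a malignant aspirate or brushing can count as a diagnostic failure

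*Combined protocol and SAP*

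**What the plan says.** Section 4.8 defines diagnostic accuracy through a list of results that count as definitive. For malignancy the criterion is "Malignancy on histological samples"; the synopsis has "Malignancy on histology". A second route takes abnormal biopsies "that are followed by a surgical lung biopsy yielding the same histological diagnosis". The benign route requires a specific histopathologic finding together with a year without malignancy. Cytology appears nowhere in the list. Nor is malignant cytology among the results named as non-diagnostic (normal or absent parenchyma, atypia, and mild or non-specific inflammation).

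On sampling, section 4.7 states for the CT arm: "Biopsy number, core biopsy vs. fine needle aspiration, use of coaxial needles, and use of rapid on-site cytologic examination will be at the discretion". The choice lies with the operator. The section sets no minimum number of samples and does not require tissue. For the bronchoscopy arm, section 4.6 states: "Biopsies will be obtained using a any-gauge needle, with at least 5 passes obtained per nodule". It adds: "Forceps biopsies, brushings or other biopsy tools will be performed according to the procedure algorithm". The procedural flow chart in section 14, where the suggested flow is detailed, is not reproduced in the text available for review.

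**The concern.** The protocol itself distinguishes core biopsy from fine needle aspiration and refers to cytologic examination, so it recognises two kinds of specimen. It then allows a procedure that may yield only one kind and writes the endpoint for the other. A patient can be sampled in full compliance, have a clearly malignant aspirate, and still meet no success criterion.

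Surgical confirmation is not a dependable rescue. It requires abnormal tissue, and whether an aspirate qualifies is not stated. It also requires an operation. Section 3.1 says that high-probability nodules are often biopsied because surgery is higher-risk or stereotactic radiotherapy is being considered, and such patients may never have surgical histology. Under section 4.9, later non-randomised biopsies do not change the result.

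The primary analysis is a difference in success rates against a 10-point margin. A loss that differs between arms shifts that difference without any change in true performance, and a loss common to both arms costs power. Because CT sampling follows local preference, scoring could also vary by site, or be settled only after results are known.

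**Working it through.** **1. The text set side by side.** Take a patient with malignant cytology only and no later surgery.
- Malignancy criterion: not met, because the specimen is not histological.
- Surgical-match criterion: not met, because there was no surgery.
- Benign criterion: not applicable.

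Success requires one of the listed routes, so absence from the non-diagnostic list does not make the case a success. The same result follows for a CT aspirate, a bronchoscopic needle pass or a brushing.

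**2. Reproducing the design.** Inputs from section 6.1: 90% in both arms, margin 0.10, one-sided 5%, 80% power.

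n = (1.645 + 0.842)² × (2 × 0.9 × 0.1) / 0.10² ≈ 111.3, so 112 per group, as stated.

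Section 6.2 gives Beta(1,1) priors and declares non-inferiority if the posterior P(NB − CT < −0.10) is below 0.05. I enumerated every pair of binomial outcomes at 112 per group, at fixed true rates.
- CT 90% / NB 80%: 5.3% (the plan's table shows 5.4%).
- 90% / 90%: 80.1% (the table shows 74.4% non-inferior plus 4.7% superior, 79.1% in all).

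Section 6.2 describes drawing the true rates from distributions with SD 0.03. That gives about 11% in the 90/80 scenario, so the fixed-rate calculation is the one that matches the printed table, and it is used below.

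**3. Effect of lost cytology-only malignancies.** The losses are assumptions; the documents give none of them. Each is subtracted from the true rate before the same rule is applied.

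| Points lost, CT | Points lost, NB | Declared non-inferior, true 90/80 | Declared non-inferior, true 90/90 |
|---|---|---|---|
| 0 | 0 | 5.3% | 80.1% |
| 2 | 0 | 11.1% | 88.9% |
| 3 | 0 | 15.3% | 92.0% |
| 5 | 0 | 25.8% | 96.1% |
| 5 | 2 | 14.6% | 88.5% |
| 5 | 5 | 5.2% | 67.4% |
| 2 | 5 | 1.3% | 45.9% |
| 0 | 5 | 0.4% | 31.1% |

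**4. What loss might arise.** Loss in an arm = f × m × u, where f is the share of the arm with cytology only, m the share of those with a malignant result, and u the share of those not confirmed at surgery. Assume m = 40–60% and u = 50–100%, with loss in CT only.
- f = 10%: from 0.10 × 0.40 × 0.50 = 2 points to 0.10 × 0.60 × 1.00 = 6 points; false non-inferiority 11% to 32%.
- f = 20%: from 4 to 12 points; 20% to 72%.

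Any loss in the bronchoscopy arm offsets this, and a larger loss there reverses it.

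**The case against.** The strongest reply is that the wording is loose and the investigators never meant to fail malignant aspirates. The title names the comparator as transthoracic needle aspiration. Section 4.7 qualifies operators through needle biopsy or aspiration. Section 4.6 calls needle passes biopsies. Frank purulence is listed as a histopathologic finding, so the term is not used strictly. Section 4.8 also has a blinded pathologist determine all diagnoses.

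This is persuasive about intent, but it does not supply a rule. The list still has no entry that a cytology-only malignancy meets. Central review does not close the gap either: the synopsis and section 4.9 send only results without malignancy for review, so under those passages the site first decides whether malignant cytology counts.

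A reader might go further and infer that the endpoint penalises the CT arm and so favours non-inferiority. The documents do not support that. The endpoint wording is the same for both arms, and the bronchoscopy arm also relies on needles and brushings. How often forceps tissue is taken depends on an algorithm that cannot be seen here, and CT operators may take cores. A tilt against CT is plausible, since that arm has no tissue requirement, but it is not shown. Some aspirates may also be rescued by surgical confirmation. This part of the objection stands in full.

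**Conclusion.** The concern holds as a defect in the endpoint definition: followed literally, the list fails valid malignant results from sampling methods that the protocol permits in both arms. Its net direction and size are not established. The inflated false non-inferiority figures (11%, 15% and 26% for 2, 3 and 5 points) assume a loss confined to CT and should not be read as this trial's error rate. Equal losses leave the error near 5% and cost power (67% at 5 points each); a 5-point loss confined to bronchoscopy leaves 31%. All of this rests on the strict reading, on assumed losses, and on fixed true rates with 112 evaluable patients per group. Under that reading, every loss pattern examined either inflates the error or reduces power, so the case for correcting the text does not depend on the direction.

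**What to change.** In section 4.8 and the synopsis, reword the malignancy criterion to: *malignancy on histology or cytology from the target nodule, obtained at the randomised procedure*, identically for both arms. Keep atypia non-diagnostic, as now written, and state that cytology which is only suspicious is also non-diagnostic in both arms. Leave the benign criterion unchanged; nothing here argues for altering it.

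Section 6.3 already records the number and type of biopsies. Refine that field to mark cytology-only results, and pre-specify a sensitivity analysis that counts tissue diagnoses only, with the cytology-only share reported by arm.

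The cost is an amendment to two passages and a small change to an existing data field. No patients or procedures are added, and the design stays at 112 evaluable per group. The downside is that cytology may carry slightly more false positives than tissue, which the tissue-only analysis would help to show.

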The diagnostic algorithm for indeterminate pulmonary nodules is based on pre-test probability of malignancy as determined by validated clinical prediction scores or clinician estimates. Low-probability (<10% chance of malignancy) are followed radiologically with serial CT, while high pre-test probability nodules (>70% chance of malignancy) are typically surgically resected, although tissue confirmation is often necessary even for these nodules.⁵ A non-surgical biopsy is typically recommended for nodules with low to intermediate probability of malignancy. High pre-test probability nodules are also frequently biopsied, when surgery is considered higher-risk or when stereotactic body radiation therapy is considered. Options include CT-guided transthoracic needle biopsy or bronchoscopic biopsy. CT-guided biopsy is associated with a general yield estimated at 90%, although studies focusing on nodules < 1.5 cm have reported yields between 70% and 80%.⁶⁻⁸ There has not been randomized controlled studies comparing CT-guided biopsy to other approaches. The technique is associated with substantial complications: in a population-based study, the rate of pneumothorax was 15% with need for chest tube management in 7%, and the risk of hemorrhage was 1%.⁹ Conversely, bronchoscopic biopsy is safer with reported 1.6% pneumothorax, with a need for chest tube management in 0.7%, and a 0.5% hemorrhage risks, but best estimates of yield using conventional navigation techniques approach 75%, with rates below 50% in registry data.¹⁰⁻¹²

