6.3 Variables Recorded

- Past medical history
- Demographic data
- Smoking history
- Occupational history
- Current medications
- Laboratory data (complete blood count, electrolytes, creatinine, coagulation profile if available, results of fungal serologies if available)
- Chest CT characteristics:
 - Location of the nodule (lobe and segment)
 - Nodule size (longest axis)
 - Distance to the nearest visible bronchus on either CT plane (axial, coronal or sagittal)
 - Bronchus sign (airway aligned with nodule)
 - Distance to the nearest parietal pleura
- PET scan characteristics (FDG uptake (SUV))
- Procedural characteristics:
 - Duration of procedure
 - Number and type of biopsies
 - Use of FluoroNav, and divergence in mm if used
 - Radiation exposure
 - Complications (pneumothorax, bleeding, others)
- Time to procedure (delay between decision to biopsy and procedure)
- Time from identification of nodule to treatment for malignant nodules
- Need for another biopsy modality
- Need for an additional staging procedure
- Follow-up data.

7. Safety Reporting of Adverse Events

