7.1 Grading

Adverse events will be graded according to the NCI's Common Terminology Criteria for Adverse Events (NCI CTCAE), Version 5.0, dated November 27, 2017, currently locatable via the following URL:
https://ctep.cancer.gov/protocoldevelopment/electronic_applications/docs/CTCAE_v5_Quick_Reference_8.5x_11.pdf

CONFIDENTIAL

If events are not listed in the CTCAE, severity may be designated as mild, moderate, severe, life-threatening, or fatal which respectively correspond to Grades 1, 2, 3, 4, and 5 on the NCI CTCAE, with the following definitions:

- **Mild:** Asymptomatic or mild symptoms; clinical or diagnostic observations only; intervention not indicated;
- **Moderate:** Minimal, local or noninvasive intervention indicated; limiting age-appropriate instrumental activities of daily living (ADL) such as preparing meals, shopping for groceries or clothes, using the telephone, managing money, etc;
- **Severe:** Medically significant but not immediately life-threatening; hospitalization or prolongation of hospitalization indicated; disabling; limiting self care ADL such as bathing, dressing and undressing, feeding self, using the toilet, taking medications;
- **Life-threatening:** Urgent intervention indicated to prevent risk of death present at the time of the event;
- **Fatal:** An event that results in the death of the patient.

Information on adverse events, whether serious or not, whether reported by the participant, directly observed, or detected by physical examination, laboratory test or other means, will be collected, recorded, followed and reported as described in the following sections.

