7.2 Reporting Period

The procedures being performed, bronchoscopy and CT-guided biopsy, are standard of care for management of indeterminate pulmonary nodules. Therefore, collection of data regarding adverse events and serious adverse events will be limited in this study:

- Any serious or non-serious adverse event related to research procedures (i.e. the consent process, HIPAA compliance, etc.) will be collected.
- After informed consent but prior to initiation of navigation bronchoscopy or CT-guided biopsy, serious and non-serious adverse events should be reported only if possibly, probably or definitely attributed by the patient's study physician to a protocol-mandated research procedure or intervention.
- The principal AE reporting period will be within 7 days of the study procedure, as it would be exceedingly uncommon for a new biopsy-related complication to occur more than 7 days after the biopsy procedure. Effort should be made on post-procedure day #7 to assess for any complications which have not already risen to investigator awareness.
- Any serious adverse event that occurs \leq 7 days after initiation of navigation bronchoscopy or CT-guided biopsy, regardless of causality to participation in the study, must be reported to the Coordinating Center in an expedited fashion as directed below (Reporting Procedures).

CONFIDENTIAL

During the 7-day reporting period, non-serious adverse events should only be recorded if, in the opinion of the investigator, there is a reasonable possibility the event is attributable to participation in the study. Non-serious adverse events related to navigation bronchoscopy or CT-guided biopsy or the next phase of the patient's treatment or management should NOT be recorded.

Participants should be instructed to report any serious post-study event(s) that might reasonably be related to participation in this study. The investigator should notify the IRB and the Coordinating Center of any unanticipated death or adverse event occurring after a participant has discontinued or terminated study participation that may reasonably be related to the study.

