7.3 Procedure-related Risks

We do not expect additional safety concerns from this protocol over those incurred during navigation bronchoscopy and CT-guided biopsy, explained to all patients undergoing navigation bronchoscopy and CT-guided biopsy as part of clinical informed consent in the standard of care setting. These risks, inherent in the procedures themselves, include pneumothorax, bleeding, pain, or, rarely, infection. Risk of death is estimated around 1/10,000. We do not expect that enrollment in this study will result in an increased risk for the patient.

The greatest risks from bronchoscopy are related to sedation and maneuvering the bronchoscope into the patient's airway. Accordingly, a nurse and/or a respiratory therapist will monitor all patients during the procedure and full anesthesia support will be available. In addition, pulse oximetry, respiratory rate, blood pressure, ECG, and heart rate will be continuously monitored. Patients will not be released until they are fully awake and medically stable as per standard local standard of care operations.

Other risks include those associated with biopsy and are the same as for standard flexible bronchoscopy: pneumothorax, breathing difficulty, vocal cord spasm, vomiting, dizziness, bronchial spasm, infection, low blood oxygen, heart attack and bleeding from biopsied site. The occurrence of these risks is extremely low. The measures to mitigate the risks are the same as for all bronchoscopy. To minimize the chance of bleeding, all patients will be questioned about tendency to bleed prior to bronchoscopy as per standard care. Anticoagulation with antiplatelet agents will be held according to guideline recommendations for that drug. If bleeding occurs, patients will be treated with direct pressure, local instillation of iced saline or other bronchoscopic interventions as deemed necessary. Vocal cord spasm will be mitigated with the use of lidocaine on the vocal cords. Patients with lung disease may receive bronchodilators prior to bronchoscopy at the discretion of the performing bronchoscopist. Patients are given supplemental oxygen and their oxygen level is continuously monitored using pulse oximetry. If there is any sign of a worsening in status, such as elevated heart rate, low oxygen, or electrocardiogram (ECG) changes, the procedure will be aborted.

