The risks associated with CT-guided biopsy include pneumothorax, breathing difficulty, infection, low blood oxygen, and bleeding from biopsied site. The predominant risk of this procedure is pneumothorax. The measures to mitigate the risks are the same for all biopsy procedures. To minimize the chance of bleeding, all patients will be questioned for their tendency to bleed prior to the procedure as per standard care.

Anticoagulation with antiplatelet agents will be held according to guideline recommendations for that drug. If bleeding occurs, patients will be treated with direct pressure. Patients are given supplemental oxygen and their oxygen level is continuously monitored using pulse oximetry. A nurse, respiratory therapist and physician continuously monitor patients ECG, heart rate, blood pressure, and blood oxygen during the procedure. If there

CONFIDENTIAL

is any sign of a worsening in status, such as a clinically significant elevated heart rate, low oxygen saturation, or ECG changes, the procedure will be aborted.

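### The clinically significant bleeding endpoint has no common severity threshold: any bleeding needing intervention counts, interventions differ by arm, and the listed data cannot separate minor from consequential bleeds

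*Combined protocol and SAP*

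**What the plan says.** The synopsis and section 4.8 list as a secondary endpoint "Clinically significant bleeding (defined by bleeding requiring intervention". Neither defines intervention or adds a grade, a volume or a clinical consequence. Section 3.2 names this comparison among those to be made between the arms.

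Section 7.3 describes the response to bleeding in each procedure:

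- Bronchoscopy: "If bleeding occurs, patients will be treated with direct pressure, local instillation of iced saline or other bronchoscopic interventions as deemed necessary".
- CT-guided biopsy: "If bleeding occurs, patients will be treated with direct pressure". Here the sentence ends, with no qualifier and no further measures.

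On data capture, section 6.3 lists "Complications (pneumothorax, bleeding, others" among the procedural characteristics, without a severity or intervention item. In section 7.2, "Any serious adverse event that occurs" within 7 days of starting the procedure is reportable whatever its cause. The same section says that "Non-serious adverse events related to navigation bronchoscopy or CT-guided biopsy or the next phase" of management are not to be recorded.

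For background rates, section 3.1 says of CT-guided biopsy that "the risk of hemorrhage was 1" per cent, and gives 0.5% for bronchoscopy.

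**The concern.** The label promises bleeding that matters clinically. The only filter is the need for an intervention, and section 7.3 plans some intervention for bleeding as such. A filter that the planned response to any bleed can satisfy does not separate consequential from trivial bleeding. The planned responses also differ by procedure, so the threshold for being counted may differ by arm for reasons unrelated to harm.

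The operator knows the procedure, and the plan describes blinded review for pathology but none for bleeding. Pneumothorax is handled better: the plan counts all events and, separately, those needing a chest tube, which is one named intervention with the same meaning in both arms. Bleeding has no such anchor.

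The stake is the safety comparison. Section 4.1 gives a likely reduction in complications as part of the reason for choosing a non-inferiority design, so readers will weigh the bleeding result beside the accuracy result.

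**Working it through.** **Inputs from the documents.** Haemorrhage risk 1% (CT) and 0.5% (bronchoscopy), section 3.1. Group sizes 112 evaluable and 129 randomized per arm, section 6.1. The plan states no sample size, power or significance test for bleeding.

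**The plan's own figure, for context.** The primary-endpoint size reproduces: with 90% in both arms, a 10-point margin, one-sided 5% and 80% power, n = (1.645 + 0.842)² × 2 × 0.9 × 0.1 / 0.1² ≈ 111.3, so 112 per group (power 80.2%). The 129 is 112 × 1.15 = 128.8, rounded up.

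**Expected bleeds, n × rate.**

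- 112 per arm: CT 112 × 0.01 = 1.12; bronchoscopy 112 × 0.005 = 0.56.
- 129 per arm: CT 1.29; bronchoscopy 0.645.

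Power to detect 1% against 0.5% (two-sided 5%) is about 6.3% at 112 and 6.7% at 129 per arm; 80% power would need 4,673 per arm. Even a perfectly defined endpoint would be descriptive here.

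**Point of reversal.** Suppose an extra share q of bronchoscopies has minor bleeding that is treated and counted, with none added in the CT arm. The expected order reverses once 0.5% + q exceeds 1%, that is, q above 0.5 percentage points. One extra patient in 112 is 0.9 percentage points.

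**Sensitivity to q, in either direction.** The documents give no minor-bleed rate, so q is an assumption and is shown as a range. Expected counts at 112 per arm:

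| Extra counted share q in one arm | Added to bronchoscopy: 112 × (0.005 + q), against CT 1.12 | Added to CT: 112 × (0.01 + q), against bronchoscopy 0.56 |
|---|---|---|
| 1% | 1.7 | 2.2 |
| 2% | 2.8 | 3.4 |
| 5% | 6.2 | 6.7 |
| 10% | 11.8 | 12.3 |

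Because section 7.3 provides treatment in both arms, both columns are possible, and so is a partial cancellation. To show how few events it takes, at 112 per arm a split of 7 against 1 gives a two-sided Fisher p of 0.065, and 8 against 1 gives 0.035.

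**Can the analysis repair it?** Only if the data distinguish minor from consequential bleeds. Section 6.3 lists bleeding as a complication and no more. Section 7.1 has a severity scale, whose fallback definition of moderate begins "Minimal, local or noninvasive intervention indicated", but nothing links it to this endpoint. The section 7.2 rule removes non-serious procedure-related events from adverse-event recording, so non-serious bleeds would not be graded. On the data the plan lists, the answer is no.

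**The case against.** Several points against the concern are fair.

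- The endpoint says requiring intervention, not receiving it, and section 7.3 is a risk narrative, not an endpoint rule. A careful investigator could exclude trivial bleeds. This stands, but it leaves the threshold to unblinded judgement without criteria at Vanderbilt and approximately 5 to 7 other sites.
- Serious bleeding is also caught through serious adverse event reporting and the separate hospitalization endpoint, and bleeding is a recorded complication whether or not it was treated. This stands. It limits the damage but does not make this endpoint's count interpretable.
- It is one of several secondary endpoints and is sparse under any definition. This also stands, and it limits the weight of the point.

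Two stronger readings are tempting, and the documents do not support them. A reader might infer that CT-arm haemorrhage goes untreated and is missed, so that the endpoint must count against bronchoscopy. Section 7.3 provides direct pressure for CT-arm bleeding without a qualifier, and the only discretionary wording is in the bronchoscopy sentence. How each kind of bleed is seen and handled in practice is not in the documents.

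A reader might also infer that false safety signals against bronchoscopy would be frequent. That requires assumed minor-bleed rates, no extra counted bleeds in the CT arm, and a significance test that the plan does not specify. The answer also moves with the test: for an assumed 5% against 1% at 112 per arm, a pooled z-test rejects in 41.2% of trials and Fisher's exact test in 24.5%.

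**Conclusion.** The concern holds as a defect in the outcome definition. The endpoint does not isolate clinically significant bleeding, its threshold can differ by procedure, and the listed data give no way to sort bleeds afterwards. No direction of bias can be claimed.

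With about one expected event per arm, a handful of minor bleeds counted in one arm would dominate the comparison, and an excess above 0.5 percentage points in the bronchoscopy arm would reverse the expected order. This rests on the section 3.1 rates applying to these patients; the documents do not say how haemorrhage was defined in the studies behind those rates. It also rests on the section 6.3 list being complete, since the case report form is not reproduced.

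The scope is one named secondary safety comparison. The primary analysis, the non-inferiority decision and the sample size are untouched. The change is worth making because it is cheap and the comparison will be read.

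**What to change.** In the synopsis and section 4.8, define the endpoint by one list of qualifying consequences or escalated interventions, identical in both arms. Examples are early termination of the procedure because of bleeding, transfusion, embolisation or surgery, and unplanned admission or escalation of care within 7 days. State that topical measures or direct pressure alone do not qualify. Record those separately, by arm, as minor treated bleeding. Add matching fields to the case report form and to the section 6.3 list.

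This defines an outcome and changes no clinical management. The cost is a short definition in two places and a few tick-boxes; for any patients already treated, the fields would have to be completed from procedure records. The downside is fewer qualifying events, so the comparison should be reported descriptively, as counts and intervals by arm. At about one expected event per arm it is descriptive already.
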